6.2.2 Secondary analyses

We will perform an additional PP analysis for secondary outcomes.

6.2.3 Sensitivity analyses

As a sensitivity analysis, we will analyse the two time points separately using the same model as described above but omitting fixed terms for the time point and the interaction between time point and learning group as well as the random term for participant. In case the primary model should not fit, we will use this approach as the primary analysis.

Morover, we will analyze individual OSCE scores of each station instead of the averaged OSCE scores over all six stations within a series. We will use the same model as described above, but using a random term for station instead of a fixed term for series. We will also consider random terms for series and assessor as well as a random slope if there is non-zero variability and if the model fits. Should models not fit, we will analyse the two time points separately.

Depending on the distribution of the additional hours of self-training, we will furthermore use a non-parametric Wilcoxon-rank-sum test, a mixed-effects negative binomial model considering zero-inflation and a random term for sites, or a negative binomial model considering zero-inflation and robust standard errors for this secondary outcome.

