3.2 Randomization

We will use centralized computed randomization in blocks of 4 to allocate each of the participants to one of the two study arms, with allocation in a 1:1 ratio, stratified by study site. The reason for block randomisation is the requirement of the control group to comprise of exactly 24 or 28 students due to the max. group size of 4 students per tutor. The randomization will be performed by an external partner (CTU Bern). An independent statistician of CTU Bern, who is not otherwise involved in the trial, will receive a list of participants of each site that contains the participant ID but no identifying data and will randomly allocate entries to either treatment arm. The generated allocation sequence will be password-protected and sent back to the trial coordinator. This procedure will ensure concealment of

allocation, i.e. randomization will be done without the influence from investigators or study personnel.

Figure 1: Study methods summary

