5.2 Eligibility

Students of human medicine at one of three Swiss universities (Bern, Freiburg, Zurich, in the 3rd to 8th semester) are eligible for study participation if they are:

- willing to participate in the study and give their consent to take part in the research;
- willing to pay the 200.- CHF course fees (partial reimbursement of tutors and administrative fee for the SGUM course certificate);
- fill out the baseline questionnaire.

Exclusion criteria for study participation are:

- Did not sign the study agreement or pay the course fee;
- More than 5 hours of previous formal ultrasound training;

• Failure to fill out baseline questionnaire.

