5.3 Recruitment

We will primarily recruit students in semester 7 in Bern (total medical student intake per year = 220), in semester 6 in Zurich (240) and Fribourg (120). A CONSORT participant flow diagram will be drawn following the CONSORT 2010 standards (http://www.consort-statement.org/consort-2010).

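### The optional Wilcoxon test of self-training hours ignores the site strata used in randomisation; it is conservative and loses some power if hours differ between sites

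*SAP*

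**What the plan says.** SAP 3.2 describes "centralized computed randomization in blocks of 4", "with allocation in a 1:1 ratio, stratified by study site". There are three sites (SAP 5.2: "Students of human medicine at one of three Swiss universities").

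Additional self-training hours are a secondary outcome (6.1.2). Their main analysis, in 6.2.1, is a quantile regression of the median whose standard errors allow for clustering by site. Section 6.2.3 then adds: "Depending on the distribution of the additional hours of self-training, we will furthermore use a non-parametric Wilcoxon-rank-sum test". Two alternatives follow, joined by 'or': a mixed-effects negative binomial model with a random site term, and a negative binomial model with robust standard errors. The "non-parametric Wilcoxon-rank-sum test" carries no stratification, and no other section of the SAP supplies one.

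**The concern.** Complete blocks within site split each site equally between the arms, so differences between sites cannot move the arm comparison. The null variance of a pooled Wilcoxon test is nevertheless computed from all the ranks, including the part of their spread that lies between sites. If sites differ, that variance is too large, the test rejects too rarely, and power is lost.

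Site differences in voluntary practice are possible. Recruitment is mainly "in semester 7 in Bern" but in semester 6 in Zurich and Fribourg (5.3), and the sites are assessed at different times to fit local timetables (3.6).

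At stake is how clearly a sensitivity check can be read. If the pooled test were non-significant beside a significant main analysis, a reader could not tell a fragile result from a test that had lost power by ignoring the design.

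**Working it through.** **The plan's own figure.** The SAP states no figure for self-training hours. Its only sample-size figure, for the primary outcome (3.3), reproduces. With SD 4, margin 1.5, assumed advantage 0.5, one-sided alpha 0.05 and power 90%, n per arm = 2 × (1.645 + 1.282)² × 4² / (1.5 + 0.5)² = 68.5, so 69 per arm and 138 in total. Then 138 / 0.91 = 151.6, so 152.

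**Inputs from the SAP.** Three sites, 1:1 allocation, blocks of 4 within site (3.2, 5.2), and two-sided 0.05 for secondary outcomes (4.1). Section 3.2 requires the "control group to comprise of exactly 24 or 28 students". Read as a per-site figure, this gives sites of 48 or 56, and 48 + 48 + 56 = 152 matches the planned total.

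**Assumed inputs.** The SAP gives no distribution of hours, no site levels and no expected arm difference. All three are assumed below and varied.

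**Formula.** Let f be the share of rank variance that lies between sites. The true null SD of the pooled statistic is √(1 − f) times the value the test uses, so

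- type I error = 2 × [1 − Φ(1.960 / √(1 − f))];
- power, where the stratified test has 80%, = Φ(1.960 + 0.842 − 1.960 / √(1 − f)).

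| f | Type I error, pooled | Power, pooled (stratified 0.80) |
|---|---|---|
| 0 | 0.050 | 0.800 |
| 0.05 | 0.044 | 0.785 |
| 0.10 | 0.039 | 0.769 |
| 0.20 | 0.028 | 0.729 |

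**Simulation 1.** Negative binomial hours (shape 1.5) with 20% extra zeros and an arm ratio of 1.7; 15,000 null runs and 6,000 power runs per row.

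| Mean hours by site | Highest/lowest | Type I, pooled | Type I, stratified | Power, pooled | Power, stratified | Loss (points) |
|---|---|---|---|---|---|---|
| 6/6/6 | 1 | 0.049 | 0.049 | 0.576 | 0.572 | none |
| 5/6/8 | 1.6 | 0.046 | 0.050 | 0.546 | 0.561 | 1.5 |
| 4/6/10 | 2.5 | 0.043 | 0.049 | 0.513 | 0.574 | 6 |
| 3/6/12 | 4 | 0.037 | 0.050 | 0.456 | 0.579 | 12 |
| 2/6/18 | 9 | 0.027 | 0.049 | 0.322 | 0.565 | 24 |

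The Monte Carlo standard error is about √(0.57 × 0.43 / 6000) = 0.006 for power. The formula agrees: at 3/6/12 the simulated f was 0.124, which gives 2 × [1 − Φ(1.960 / √0.876)] = 0.036 against 0.037 simulated. With 9% of students missing at 3/6/12, type I error is 0.039 pooled against 0.051 stratified, and power 0.41 against 0.52.

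**Simulation 2.** Log-normal hours (median about 4, log-SD 0.9, rounded down) with an arm ratio of 1.5; 4,000 to 6,000 runs per row.

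| Ratio of site medians | Highest/lowest | Type I, pooled | Power, pooled | Power, stratified |
|---|---|---|---|---|
| 1:1:1 | 1 | 5.2% | 77% | 77% |
| 0.8:1:1.25 | 1.6 | 4.6% | 75.5% | 76% |
| 1:1:1.5 | 1.5 | 4.7% | 75% | 76% |
| 0.67:1:1.5 | 2.2 | 3.9% | 72% | 77% |
| 0.5:1:2 | 4 | 2.0% | 63% | 77% |
| 0.33:1:3 | 9 | 0.4% | 41% | 75% |

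At the same 4-fold ratio, the type I error is 3.7% under the first distribution and 2.0% under the second. The numbers therefore depend on the assumed distribution; the direction does not.

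**The case against.** The strongest reply is that this test decides nothing. The estimate, interval and p-value for self-training hours come from the quantile regression in 6.2.1. The Wilcoxon test is one of three options and may never be run. A reader might infer that a real difference in self-training could be missed, or that the secondary outcome is analysed with too little power. The SAP does not support that: the loss concerns a conditional back-up, and the outcome has no power target. This part of the reply stands in full.

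A reader might also infer that the test is bound to be undersized, or that losses of 14 or 34 points (77% to 63%, 75% to 41%) are to be expected. Those follow from 4-fold and 9-fold site ratios, for which the SAP gives no basis. Two of the three sites recruit from the same semester, and different assessment dates do not by themselves imply multi-fold differences in practice. This also stands.

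Third, the SAP does not handle site uniformly in any case. The last negative binomial option names no site term. As described, the quantile regression uses site only for its standard errors, so it compares overall medians. A pooled rank test mirrors that comparison, whereas a stratified test addresses a shift within sites. This is a fair point about the question being asked, and it is a small cost of the change. It does not remove the mismatch between a pooled variance and an allocation balanced within site.

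**Conclusion.** The point holds as a minor improvement. The Wilcoxon test named in 6.2.3 does not follow the stratified allocation in 3.2, and it is conservative and less powerful whenever hours differ between sites. Under the assumed data the loss is nil with equal sites, about 1 to 6 points of power for mild to moderate differences (levels up to about 2.5-fold apart), and 12 points or more at 4-fold and above. The stratified test kept its size at about 5% and lost no appreciable power when sites were equal.

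The conclusion rests on reading the 24 or 28 controls as per site and on assumed distributions, arm effects and site levels. It does not concern the main analysis of this outcome, the sample size or the primary non-inferiority conclusion, and no false-positive claim can result from it.

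**What to change.** In SAP 6.2.3, replace the Wilcoxon rank-sum test with a Wilcoxon rank-sum test stratified by study site (van Elteren). In each site, take the rank sum minus its null expectation; add these with weights 1/(site size + 1); divide by the square root of the sum of the squared weights times the site variances.

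The cost is a short edit before the analysis, with no new data and no change to any other analysis. The one thing given up is the pooled comparison, since the stratified test addresses a shift within sites; the SAP should say so in a sentence.

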6.2.4 Additional analyses

We will explore the association of different factors such as gender, hours of additional training, motivation for ultrasound and mean group size with OSCE scores six months after the course using multivariable mixed-effects linear models with robust standard errors.

6.2.5 Assessment of statistical assumptions

We will assess normality and homoskedasticity of residuals of the linear model used to analyse OSCE scores based on a QQ-plot as well as a fitted-value vs. residual plot. If the distribution severely deviates from a normal distribution, we will perform adequate transformation of OSCE scores.

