3.3 Sample size

Based on a pilot with 20 students we expect a mean score of 33 out of 50 points per station with a standard deviation (SD) of 4 points. The study was powered for noninferiority using a margin of -1.5 points for the difference in mean OSCE score between the intervention and control group in the practical exam at 6 months (primary outcome). A difference of 1.5 points would correspond to an effect size of 0.375 standard deviations (SD), which we would still consider as non-inferior. We calculated the sample size with the assumption that the intervention group will

perform somewhat better (+0.5 points in mean OSCE score) than the control group based on test

results from previous pilots. We chose a one-sided alpha-error of 0.05 and a power of 90% which yielded 138 participants (69 in each arm). Allowing for a 9% dropout rate we decided to include 152 students.

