6.2 Analysis methods

6.2.1 Primary analysis

As recommended by the CONSORT statement for non-inferiority trials, we will perform both intention-to-treat (ITT) and per-protocol (PP) analyses. For the primary outcome, ITT and PP analyses must reach the same conclusion to establish noninferiority. For secondary outcomes, the ITT analysis will be the primary analysis, the PP analysis a secondary analysis.

We will use a repeated-measures mixed-effects linear model with robust standard errogrs to compare the mean OSCE scores of both groups 6 months after the course (primary outcome) as well as immediately after the course (secondary outcome), taking into account the possible dependence of data within sites, participants, and series. The model will include the averaged OSCE score over all six stations of a series of each participant at both time points as dependent variable, fixed terms for the learning group, the type of series, the time point and the interaction term between learning group and time point, and random terms for site and participant. We will assess non-inferiority based on a one-sided 95% confidence interval for the difference in mean OSCE score between the two groups 6 months after the course. If the lower confidence limit lies above the non-inferiority margin of -1.5 points, we will claim non-inferiority. If non-inferiority can be established, we will test for superiority of the blended learning group at a two-sided alpha level of 0.05. This stepwise testing approach will keep the overall family-wise type-I error rate at the nominal 5%-level.

The difference in mean OSCE score immediately after the course will be assessed from the same model described above and presented with a two-sided 95% confidence interval and corresponding p-value.

The difference in median number of additional hours of self-training will be assessed from a quantile regression using robust standard errors to account for dependence of data within sites, and presented with a two-sided 95% confidence interval and corresponding p-value.

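### SAP 6.2.5 allows an unspecified transformation of OSCE scores without exempting the primary model, although the -1.5 margin is defined only in raw points

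*SAP*

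**What the plan says.** Section 3.3 sets the margin in points: "The study was powered for noninferiority using a margin of -1.5 points for the difference in mean OSCE score". The planning values are on the same scale: "we expect a mean score of 33 out of 50 points per station with a standard deviation (SD) of 4 points", with the intervention group assumed to "perform somewhat better (+0.5 points in mean OSCE score) than the control group". The same section also expresses the margin as 0.375 SD, which is 1.5/4 and so only restates the raw margin.

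The decision rule in section 6.2.1, repeated in section 4.1, is in points too: "If the lower confidence limit lies above the non-inferiority margin of -1.5 points, we will claim non-inferiority". Table 2 defines the outcome as the average of station scores running from 0 to 50. The primary model is a repeated-measures mixed linear model with robust standard errors, and ITT and PP must agree before non-inferiority is claimed.

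Section 6.2.5 then has the residuals of the linear model for OSCE scores checked by QQ-plot and by a plot of residuals against fitted values, and adds: "If the distribution severely deviates from a normal distribution, we will perform adequate transformation of OSCE scores".

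**The concern.** The linear model for OSCE scores includes the primary model, and section 6.2.5 makes no exception for it. A linear rescaling cannot cure non-normality, so any transformation that serves the stated purpose is non-linear. After it, the group coefficient is no longer a difference in mean points. A log model, for example, estimates a ratio of geometric means. A limit on that scale cannot be set against -1.5 points.

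The SAP gives no threshold for a severe deviation, no list of acceptable transformations and no margin for any other scale. These choices would be made after looking at outcome residuals. Nothing keeps ITT and PP on one scale if their plots differ, although the two must reach the same conclusion. What is at stake is the pre-specification of the trial's main claim, and of the superiority test that follows only if non-inferiority is shown.

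**Working it through.** **1. The plan's own figure, on the raw scale.** Inputs from section 3.3: margin 1.5, SD 4, assumed true difference +0.5, one-sided alpha 0.05, power 90%. The distance from the assumed difference to the margin is 0.5 + 1.5 = 2.0 points.

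- n per arm = 2 × SD² × (z₀.₉₅ + z₀.₉₀)² / 2.0² = 2 × 16 × (1.645 + 1.282)² / 4 = 68.5, rounded up to 69; total 138.
- With 9% dropout: 138 / 0.91 = 151.6, rounded up to 152.
- Power at 69 per arm: SE = 4 × √(2/69) = 0.681; 2.0/0.681 − 1.645 = 1.292; power 90.2%.

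The stated 138 and 152 are reproduced. The design rests on raw points throughout.

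**2. What 1.5 points becomes after a transformation.** For a transformation g and control mean m, the equivalent of the margin is g(m − 1.5) − g(m). Only m = 33 comes from the SAP; 28 and 38 are assumed, to show the dependence.

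| Scale | m = 28 | m = 33 | m = 38 |
|---|---|---|---|
| log: ln((m − 1.5)/m) | -0.055 | -0.047 | -0.040 |
| square: (m − 1.5)² − m² | -81.75 | -96.75 | -111.75 |

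On logit(x/50), at 25, 33 and 41 (the first and last again assumed), the values are -0.120, -0.131 and -0.191. The equivalent shrinks with m on the log scale and grows on the other two, so no single converted margin stands for 1.5 points. These conversions are taken at the mean. A transformed model compares means of transformed scores, so the spread within each arm would matter as well.

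**3. The same dependence expressed in points.** Suppose the log margin were fixed at the planning mean, a ratio of 31.5/33. At a control mean of 28 it would allow a loss of 28 × 1.5/33 = 1.27 points, and at 38 a loss of 38 × 1.5/33 = 1.73 points, instead of 1.5.

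**4. Whether the raw scale is safe.** A simulation used 69 per arm, a true difference of exactly -1.5, SD 4, an unequal-variance standard error and 40,000 runs. The one-sided type I error was 0.051 with normal scores and 0.050 with strongly left-skewed (exponential-shaped) scores, against a nominal 0.05. This is a two-group comparison with the same shape in both arms. It does not reproduce the three-site mixed model or arms with different shapes.

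**The case against.** The strongest reply is that section 6.2.5 does not say that the transformed analysis replaces the raw-scale test. Where this SAP means a fallback to become primary, as for a primary model that does not fit (section 6.2.3), it says so. Sections 4.1 and 6.2.1 state the rule in points with no distributional condition. That stands in part: the text leaves the relation open and does not plainly order a margin test on another scale. But the rule covers the model on which the margin is tested, without exemption, so the other reading is at least as natural.

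Second, the trigger may never be met. The outcome averages six stations, is expected near 33 with SD 4, and so sits (50 − 33)/4 = 4.25 SD below the ceiling. This makes the defect conditional. It does not remove it, since distance from the ceiling does not exclude a long lower tail or outliers.

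Third, a reader might infer that the primary hypothesis becomes untestable. The document does not support that: the raw-scale model with robust standard errors can still be fitted, and predictions from a transformed model could in principle be turned back into a mean difference in points. The SAP plans no such step, however.

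Fourth, a reader might apply the number -1.5 to the log scale and conclude that a score 78% lower would pass, since 1 − exp(-1.5) = 0.78. The SAP always attaches the word points to its margin and nowhere suggests this.

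**Conclusion.** The point holds in a limited form. If section 6.2.5 is triggered for the primary model, the decision rule cannot be applied to the transformed scores, and both the transformation and any substitute margin would be chosen after seeing the data. The dependence on the control mean is algebraic. Its size here (on the log scale -0.055 to -0.040 around -0.047, or 1.27 to 1.73 points instead of 1.5) rests on the assumed means of 28 and 38 and does not show that the trial's conclusion would change by that amount. The sample size is unaffected. Because the problem arises only after a severe deviation and the raw-scale test remains available, it should be fixed before the data are analysed but does not undermine the design.

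**What to change.** Add to section 6.2.5 that the primary non-inferiority analysis, in both ITT and PP, always uses untransformed OSCE points. If residuals are severely non-normal or heteroskedastic, keep the estimated mean difference and take the one-sided 95% limit either from the robust standard errors already planned in section 6.2.1 or from a bootstrap that resamples participants within site and arm. Name one of the two now, so that this choice does not depend on the data either. Limit transformed analyses to supportive or sensitivity use, never for comparison with the margin.

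Deleting the transformation rule altogether is not necessary. Pre-specifying a transformation with its own margin, or a model-based conversion back to points, would also close the gap but needs more justification. The cost is one sentence and, if the bootstrap is chosen and triggered, one extra run. The planned 138 participants (152 with dropout) and the margin stay as they are.

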6.3 Missing data

If the OSCE score of at least one station at either time point (immediately after or six months after the course) is available, repeated-measures models properly account for missing data. If more than 5% of students have completely missing

outcome data at both time points, we will perform multiple imputation in the primary analysis, and perform an available case analysis as sensitivity analysis. Chained equations will be used to impute missing data, using predictive mean matching for continuous/ordinal variables, logistic regression for binary variables, and multinomial logistic regression for categorical variables. The following variables will be considered in the imputation model: OSCE score, site, station, hours of additional training, motivation for ultrasound, age, gender, and other baseline variables listed in Table 1. The two learning groups will be imputed separately. We will generate 50 imputed data sets, which will be analysed and combined using Rubin's rule.

For the secondary outcome of additional hours of self-training, we will also use multiple imputation if the primary outcome was analysed using multiple imputation. Else, we will disregard missing data and perform an available case analysis.

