6.1.2 Secondary outcomes

- students' OSCE scores immediately after their courses (mean score); see description above
- additional hours of self-training during the follow-up phase;

Table 2:	Derivation	of primar	v and sec	condary	outcomes.
	20111011011	0. p	,		

Outcome	eCRF sheet	Variable	Variable type	Derivation	Outcome type
Primary: OSCE score six months after course	Excel sheet output from electronic data entry (iPad)	Subscores at OSCE stations 1-12	Numeric	Sum of scores at individual stations (0-50 pts) divided by number of stations	Continuous
OSCE score immediately after course	Excel sheet output from electronic data entry (iPad)	Subscores at OSCE stations 1-12	Numeric	Sum of scores at individual stations (0-50 pts) divided by number of stations	Continuous
Additional hours of self-training	Online Survey before 2 nd OSCE (RedCap)	Survey questions asking on additional self-training	Numeric	Simple number between e.g. 0-100 hours	Continuous

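### The one-station premise in SAP 6.3 does not fit the averaged-score primary model, and the imputation trigger leaves 6-month losses uncovered if the separate-time-point model becomes primary

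*SAP*

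**What the plan says.** - **Score.** Table 2 in SAP 6.1.2 derives the OSCE score as "Sum of scores at individual stations (0-50 pts) divided by number of stations". It gives no rule for a series in which a station was not scored.
- **Primary model (6.2.1).** The dependent variable is "the averaged OSCE score over all six stations of a series of each participant", at both time points, with random terms for site and participant.
- **Missing data (6.3).** If at least one station score at either time point "is available, repeated-measures models properly account for missing data". The imputation rule counts only students with no outcome at either OSCE: if they exceed 5% with completely missing "outcome data at both time points, we will perform multiple imputation in the primary analysis".
- **Fallback (6.2.3).** Each time point is modelled alone, without the participant term. This is first a sensitivity analysis, but it can be promoted: "In case the primary model should not fit, we will use this approach as the primary analysis". Section 6.3 has no separate imputation rule for that case.
- **Station-level model (6.2.3).** It appears only as a sensitivity analysis.
- **Analysis sets (4.3).** The full analysis set is all randomised students. The per-protocol set leaves out students who did not attend both exams.

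**The concern.** There are two separate gaps.

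First, the premise in 6.3 describes a model that receives one record per station. The primary model receives one record per student and time point. Averaging happens before the model is fitted, so the likelihood has no information on which stations are absent. The statement therefore gives no protection for a partly scored series, and the score itself is undefined there.

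Second, the trigger is matched to the repeated-measures model but is not re-stated for the fallback. In the fallback, a student who sat the first OSCE and missed the 6-month one is dropped, and the first score is not used. Such a student never counts towards the 5%. The 6-month score is the primary outcome. If weaker students are lost more often from the blended-learning arm, the observed difference moves towards a non-inferiority claim.

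The requirement in 6.2.1 that intention-to-treat and per-protocol analyses agree does not catch this. In the fallback both analyses omit the students without a 6-month score: the first because the model drops them, the second by definition.

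**Working it through.** **1. The plan's own figures.** The inputs from SAP 3.3 are a mean of 33 with SD 4, a margin 1.5 points below control, and an assumed true difference of +0.5 in favour of the blended course. The stated result is: "We chose a one-sided alpha-error of 0.05 and a power of 90% which yielded 138 participants (69 in each arm".

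n per arm = 2 × (1.645 + 1.282)² × 4² / (1.5 + 0.5)² = 68.5, so 69 per arm and 138 in total. With 9% dropout, 138 / 0.91 = 151.6, so 152. Both figures reproduce. The sample size is not in dispute.

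**2. The trigger.** 5% of 152 is 7.6, so at least 8 students must lack both OSCEs. The planned 9% of 152 is 13.7, about 14 students. If all 14 attend the first OSCE and miss the second, the quantity counted is 0 of 152 and no imputation follows. The same holds at any rate of loss that falls only on the 6-month exam.

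**3. An incomplete series.** Table 2 allows two readings when a station is missing.

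- Fixed divisor of six: a student at the planned mean with one station unscored gets 5 × 33 / 6 = 27.5, which is 5.5 points too low.
- Divisor equal to the stations scored: the score shifts by however much easier or harder those stations are than the average of the six, and a one-station mean is treated like a six-station mean.

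The model corrects neither.

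**4. Complete-case bias in the fallback.** None of the following inputs except the SD and the margin comes from the SAP; they are assumptions.

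- 76 students per arm (152 / 2), SD 4 at each OSCE, true difference at the margin of -1.5.
- Correlation ρ between the two OSCEs: 0.1 to 0.8.
- The log-odds of missing the 6-month OSCE rise by 1 or 2 for each SD that the first score is lower. The intercept is set to give the stated loss in each arm.
- Loss of 12% vs 6%, or 15% vs 3% (blended vs control).

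Bias is the difference between the arms in the mean selection effect on the 6-month score, from 2,000,000 simulated students. SE = √(v₁ / (76(1 − m₁)) + v₀ / (76(1 − m₀))), with v the variance among those observed and m the proportion missing. It comes to 0.65 to 0.68. One-sided type I error = 1 − Φ(1.645 − bias / SE).

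| Missing | ρ | Slope 1: bias, type I error | Slope 2: bias, type I error |
|---|---|---|---|
| 12% vs 6% | 0.1 | +0.02, 5.3% | +0.03, 5.5% |
| 12% vs 6% | 0.4 | +0.08, 6.4% | +0.12, 7.1% |
| 12% vs 6% | 0.6 | +0.12, 7.2% | +0.18, 8.5% |
| 12% vs 6% | 0.8 | +0.16, 8.1% | +0.24, 10.2% |
| 15% vs 3% | 0.1 | +0.04, 5.7% | +0.06, 6.0% |
| 15% vs 3% | 0.4 | +0.17, 8.1% | +0.25, 10.0% |
| 15% vs 3% | 0.6 | +0.25, 10.1% | +0.37, 13.8% |
| 15% vs 3% | 0.8 | +0.33, 12.6% | +0.49, 18.8% |

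Example, 12% vs 6% at ρ = 0.6, slope 1: 0.12 / 0.67 = 0.18; 1 − Φ(1.645 − 0.18) is about 7%.

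With 9% missing in each arm and the same pattern, bias is 0 and the error rate is 5.0%. If the first score is used (regression of the 6-month score on the first, which is what the repeated-measures likelihood or an imputation containing it does), the bias is below 0.01 in every row.

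**The case against.** The strongest defence is that the designated primary model does handle a missed 6-month OSCE. A student with a first score stays in the repeated-measures likelihood, and under missing at random the group difference at 6 months is estimated without bias. Only students missing both exams contribute nothing, and those are the ones the trigger counts. This stands. A reader might infer that the trigger is wrong altogether; the SAP does not support that.

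Other points that stand in part:

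- **The fallback is conditional, and may coincide with low correlation.** It removes the participant term and keeps site, so it mainly cures non-fit caused by a participant variance near zero. The OSCE correlation is then low and the bias small, as the ρ = 0.1 rows show. Non-fit can have other causes, and the SAP does not define it, so the gap remains.
- **Differential loss is assumed.** SAP 3.3 gives one overall dropout rate, with no split by arm or by exam. SAP 5.4 says students who do not finish training still sit both OSCEs.
- **The trigger can fire.** Students who leave during the course would miss both exams and would count. If they pass 5%, imputation runs with the OSCE score in its model. It would be too strong to say that the fallback can never be protected; the point is that it need not be.
- **Incomplete series may be rare.** A reader might infer that a student with one station enters the model as that station's score with full weight. The SAP does not say so; it is silent. Assessors are blinded (3.8), and station loss unrelated to arm would add noise rather than bias the group difference.

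**Conclusion.** The point holds, in two limited parts.

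The one-station statement is wrong for the averaged-score primary model and right in kind only for the station-level sensitivity model. The SAP leaves the score undefined when a series is incomplete.

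The both-exams trigger is adequate for the repeated-measures model under missing at random and inadequate if the separate-time-point model becomes primary. In that case, under the assumed differential loss and correlations of 0.4 to 0.8, complete-case bias is about +0.1 to +0.5 points and one-sided type I error about 6% to 19%. The upper end needs strong selection, high correlation and 15% vs 3% loss together. At correlation 0.1 the error rate is 5% to 6%, and with equal loss and the same pattern there is no bias. These sizes rest on assumed loss patterns and correlations, not on the documents. They show what the fallback permits, not what is expected.

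A reader might conclude that the main non-inferiority analysis is compromised. It is not: harm is confined to the fallback and to partly scored series. This should be fixed because the repair is cheap and the primary conclusion may rest on the fallback, but it is not a fatal fault.

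**What to change.** - **In 6.3,** restrict the one-station statement to the station-level model. For the averaged-score model, state that missing stations are imputed within arm from the student's other stations and the other OSCE, and that the average is taken afterwards. Add the same rule to Table 2.
- **In 6.2.3 and 6.3,** state that whenever the separate-time-point model is the primary analysis, missing 6-month scores are multiply imputed with the first OSCE score in the imputation model. In that case the trigger is the proportion of missing 6-month scores.
- **Leave the existing trigger** in place for the repeated-measures model, and say that it relies on missing at random.

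The cost is SAP wording and slightly more analysis code. Chained equations, 50 data sets and imputation by arm are already specified in 6.3. No change to the sample size, data collection or conduct is needed.
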